12.3.6.2 Secondary estimand for the continuous secondary endpoints: 'treatment policy'

The secondary estimand for the continuous secondary endpoints will be:

• Treatment difference in change from baseline to Week 16 in SCORAD and DLQI, respectively, between tralokinumab+TCS and placebo+TCS regardless of rescue medication use and treatment discontinuation.

The secondary estimand assesses the average difference in change from baseline in SCORAD and DLQI after 16 weeks, resulting from initiation of a treatment regimen with tralokinumab+TCS and additional rescue medication as compared to a treatment regimen with placebo+TCS and additional rescue medication.

Trial ID: LP0162-1339	Date: 29-Aug-2018	Version: 4.0
		Page 95 of 129

Primary analyses for the secondary estimand (continuous secondary endpoints)

Data retrieved at Week 16 for subjects who have permanently discontinued IMP prior to Week 16 will be included in the analysis. Missing Week 16 data will be imputed using multiple imputations assuming that data is missing at random within the groups used for imputation.

Imputation of missing data at Week 16 will be done using multiple imputations within 4 groups defined according to randomised treatment arm and whether or not subjects have discontinued treatment prior to Week 16. Within a given treatment arm, retrieved data from discontinued subjects will be used to impute missing data for other discontinued subjects. Similarly, the available data from not discontinued subjects will be used to impute data for such subjects where the Week 16 value is missing.

For not discontinued subjects, the stepwise multiple imputations procedure will be conducted in the same way as specified for the imputation of the underlying EASI values in the primary analysis of the secondary estimand for the binary endpoints.

For discontinued subjects, it is expected that the number of subjects with retrieved data at Week 16 will be too small to facilitate the same imputation model as mentioned just above. Consequently, an imputation model with only region and baseline effects (IGA as a factor and baseline SCORAD / DLQI as a covariate) will be applied for discontinued subjects. Some factors may have to be omitted, depending on the observed data, e.g. if retrieved subjects only come from one region or if they all have the same baseline severity.

Each of the 100 imputed datasets will be analysed as described in the sensitivity analyses for the primary estimand for the continuous secondary endpoints.

Sensitivity analyses for the secondary estimand (continuous secondary endpoints)

Rather than assuming that observations are missing at random, it is assumed that missing data from subjects in the tralokinumab+TCS arm who have/have not discontinued treatment prior to Week 16 will resemble data from subjects from the placebo+TCS arm who have/have not discontinued treatment prior to Week 16.

Imputation of missing data at Week 16 will be done using a pattern mixture model where missing data in the tralokinumab+TCS arm as well as the placebo+TCS arm will be imputed from the placebo+TCS arm (copy-reference approach). With this exemption, the multiple imputation procedure and analysis will be conducted in the same way as described for the primary analysis of the secondary estimand for the continuous secondary endpoints.

Trial ID: LP0162-1339	Date: 29-Aug-2018	Version: 4.0
		Page 96 of 129

12.3.7 Analysis of additional secondary endpoints

Initial treatment period

The analysis of the below additional secondary endpoints will be based on the primary analyses of the primary estimand as specified above for the relevant primary dichotomous endpoints and continuous secondary endpoints, respectively.

The following dichotomous additional secondary endpoints will be analysed according to the primary analysis of the primary estimand for the primary endpoints:

- EASI50 at Week 16.
- EASI90 at Week 16.
- SCORAD50 at Week 16.
- SCORAD75 at Week 16.
- Reduction from baseline (Y/N) of DLQI of ≥4 points (in subjects with baseline DLQI ≥4) at Week 16.

The change from baseline to Week 16 in EASI score and the change from baseline to Week 16 in Worst Daily Pruritus NRS weekly average will be analysed according to the primary analysis of the primary estimand for the continuous secondary endpoints.

To evaluate the efficacy related to health care resource utilisation, the amount of TCS used (assessed as the amount of TCS used between visits), and the number of days without topical treatment use (collected as Patient Days of Topical Treatment Use in the eDiary) will be determined by 2-week periods. The amount of TCS used and the number of days without topical treatment use will each be analysed by a repeated measurements model with an unstructured covariance matrix and the mean modelled as follows:

 $Y = treatment \times visit + region + baseline IGA$

Results obtained after initiation of rescue treatment will be excluded from the analyses.

AD flares will be summarised descriptively as the proportion of subjects having had AD flares at Week 16, the number of AD flares from baseline to Week 16, and the rate of AD flares from baseline to Week 16. The rate of AD flares will be defined as the number of AD flares divided by time at risk, where the time at risk for each subject is the time from treatment start to last visit attended up to Week 16.

Trial ID: LP0162-1339	Date: 29-Aug-2018	Version: 4.0
		Page 97 of 129

Continuation treatment period

To support the maintenance objective of the trial, IGA of 0/1 at Week 32 among subjects with IGA of 0/1 at Week 16 and EASI75 at Week 32 among subjects with EASI75 at Week 16, both after initial randomisation to tralokinumab, will be summarised descriptively by treatment group of the continuation treatment period.

To support the maintenance objective of the trial, IGA 0/1, EASI75, EASI50, EASI90, SCORAD75, and SCORAD50, all at Week 32, will be summarised descriptively by treatment group of the continuation treatment period.

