8.2 Inclusion criteria

- 1. Written informed consent and any locally required authorisation obtained from the subject prior to performing any protocol-related procedures, including screening evaluations.
- 2. Age 18 and above.
- 3. Diagnosis of AD as defined by the Hanifin and Rajka (1980) criteria for AD (21; Appendix 4).
- 4. History of AD for ≥ 1 year.
- 5. Subjects who have a recent history (within 1 year before the screening visit) of inadequate response to treatment with topical medications.
 - Inadequate response is defined as failure to achieve and maintain remission or a low disease activity state (comparable to IGA 0=clear to 2=mild) despite treatment with a daily regimen of TCS of medium to higher potency (±TCI as appropriate), applied for at least 28 days or for the maximum duration recommended by the product prescribing information (e.g., 14 days for super-potent TCS), whichever is shorter.
 - Subjects with documented systemic treatment for AD in the past year are also considered as inadequate responders to topical treatments and are potentially eligible for treatment with tralokinumab after appropriate washout.
- 6. AD involvement of ≥10% body surface area at screening and baseline (visit 3) according to component A of SCORAD.
- 7. An EASI score of \geq 12 at screening and 16 at baseline.
- 8. An IGA score of ≥ 3 at screening and at baseline.

Trial ID: LP0162-1339	Date: 29-Aug-2018	Version: 4.0
		Page 40 of 129

- 9. A Worst Daily Pruritus numeric rating scale (NRS) average score of ≥4 during the week prior to baseline.
 - Worst Daily Pruritus NRS at baseline will be calculated from daily assessments of worst itch severity (Worst Daily Pruritus NRS) during the 7 days immediately preceding randomisation (Day -6 to 0). A minimum of 4 Worst Daily Pruritus NRS scores out of the 7 days is required to calculate the baseline average score. For subjects who do not have at least 4 scores reported during the 7 days immediately preceding the planned randomisation date, randomisation should be postponed until this requirement is met, but without exceeding the 6 weeks' maximum duration for screening.
- 10. Subjects must have applied a stable dose of emollient twice daily (or more, as needed) for at least 14 days before randomisation.
- 11. Women of child-bearing potential must use a highly effective* form of birth control (confirmed by the investigator) throughout the trial and at least for 16 weeks (5 half-lives) after last administration of IMP.

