10.2.5 Body surface area involvement

The total BSA affected by AD will be assessed by the investigator for each section of the body as component A of SCORAD (see Section 10.3.1.3) and will be reported as a percentage of all major body sections combined. The following body regions will be assessed (brackets show the highest possible score for each region): head and neck (9%), anterior trunk (18%), back (18%), upper limbs (18%), lower limbs (36%), and genitals (1%). The total BSA score will be assessed according to the schedule of procedures (Section 4).

Trial ID: LP0162-1339	Date: 29-Aug-2018	Version: 4.0
		Page 65 of 129

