10.3 Efficacy assessments

10.3.1 Investigator assessments

10.3.1.1 Investigator's Global Assessment

The IGA is an instrument used in clinical trials to rate the severity of the subject's global AD and is based on a 5-point scale ranging from 0 (clear) to 4 (severe) (Panel 6). The IGA score will be assessed according to the schedule of procedures (Section 4). The assessment will be based on the condition of the disease at the time of evaluation and not in relation to the condition at a previous visit. Whenever possible, the IGA should be assessed by the same investigator at each visit to reduce inter-rater variability. The IGA is included in the efficacy assessment & C-SSRS manual.

Panel 6 Investigator's Global Assessment

Score	Disease severity	Standard IGA scale	IGA morphological descriptors
0	Clear	No inflammatory signs of atopic dermatitis.	No erythema and no elevation (papulation/infiltration).
1	Almost clear	Just perceptible erythema, and just perceptible papulation/infiltration.	Barely perceptible erythema and/or minimal lesion elevation (papulation/infiltration) that is not widespread.
2	Mild disease	Mild erythema and mild papulation/infiltration.	Visibly detectable, light pink erythema and very slight elevation (papulation/infiltration).
3	Moderate disease	Moderate erythema and moderate papulation/infiltration.	Dull red, clearly distinguishable erythema and clearly perceptible but not extensive elevation (papulation/infiltration).
4	Severe disease	Severe erythema and severe papulation/infiltration.	Deep/dark red erythema, marked and extensive elevation (papulation/infiltration).

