12.3.6.1 Primary estimand for the continuous secondary endpoints: 'hypothetical'

The primary estimand for the continuous secondary endpoints will be:

Trial ID: LP0162-1339	Date: 29-Aug-2018	Version: 4.0
		Page 93 of 129

 Treatment difference in change from baseline to Week 16 in SCORAD and DLQI, respectively, if all subjects adhered to the treatment regimen in the sense that they did not discontinue IMP permanently and no rescue medication was made available before Week 16.

The primary estimand assesses the expected benefit when adhering to the treatment regimen tralokinumab+TCS with no rescue medication as compared to a treatment regimen with placebo+TCS with no rescue medication.

Primary analysis of the primary estimand (continuous secondary endpoints)

Data collected after permanent discontinuation of IMP or after initiation of rescue medication will not be included in the analysis.

The endpoints will be analysed using a repeated measurements model on the post baseline responses up to Week 16 with an unstructured covariance matrix, Kenward-Roger approximation to estimate denominator degrees of freedom, and the mean modelled as follows (shown for change from baseline in SCORAD):

Change from baseline in SCORAD

= treatment × visit + baseline SCORAD × visit + region + baseline IGA

This model assumes that data is missing at random within each treatment arm. The estimates will be presented with nominal p-values and 95% CI at each visit. The primary comparison between tralokinumab+TCS and placebo+TCS will be at Week 16.

Sensitivity analysis for the primary estimand (continuous secondary endpoints)

Rather than assuming that observations are missing at random within each treatment arm it is assumed that missing data from subjects who discontinue treatment/receive rescue medication in the tralokinumab+TCS arm will resemble data from subjects from the placebo+TCS arm who do not discontinue treatment/receive rescue medication. Imputation of missing data at Week 16 will be done using a pattern mixture model where missing data in the tralokinumab+TCS arm as well as the placebo+TCS arm will be imputed from the placebo+TCS arm (using a so-called copy-reference approach). The procedure for the change from baseline in SCORAD at Week 16 is described below. The same procedure will be applied for the DLQI endpoint.

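### The TCS-amount model in Protocol 12.3.7 omits the baseline extent of disease collected on every subject and takes grams between visits as two-week amounts, so precision is likely lost

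*Protocol*

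**What the plan says.** Protocol 12.3.7 (initial treatment period) covers two resource-use endpoints by two-week period: the amount of TCS used and the number of days without topical treatment. It states: "The amount of TCS used and the number of days without topical treatment use will each be analysed by a repeated measurements model". The covariance is unstructured, and the mean is treatment × "visit + region + baseline IGA". The amount of TCS is "assessed as the amount of TCS used between visits".

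Other sections that bear on this:

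- **Baseline extent is collected on everyone.** In section 8.2, inclusion criterion 6 sets a minimum involved "body surface area at screening and baseline (visit 3) according to component A of SCORAD". Criterion 7 sets EASI thresholds of "12 at screening and 16 at baseline". Section 10.2.5 adds: "The total BSA affected by AD will be assessed by the investigator".
- **Where the cream goes.** Sections 7.1 and 9.1.3.2 direct the supplied TCS to active lesions, as needed.
- **What IGA carries.** Eligible subjects have IGA 3 or 4. Panel 6 (10.3.1.1) describes mainly the intensity of erythema and papulation, with some wording on extent: grade 3 has "clearly perceptible but not extensive elevation".
- **Comparison model.** Section 12.3.6.1 models change in SCORAD (and DLQI likewise) as "treatment × visit + baseline SCORAD × visit + region + baseline IGA".
- **Visit timing.** Panel 2 gives ±3 days for Weeks 2 to 16 and no window at baseline. Its footnote 2 plans later visits relative to baseline.

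**The concern.** If the cream is spread on lesions, a subject with a larger affected area can be expected to use more of it. Area at entry can vary widely from 10% upward, and EASI can run from 16 to its maximum of 72. A two-level IGA captures only part of that spread. Whatever part of grams used could be predicted from baseline extent stays in the residual and widens the confidence interval.

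The second source of noise is calendar length. A subject who uses the same number of grams each day contributes a smaller or larger two-week amount depending only on when the visits fell.

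What is at stake is the width of the interval for TCS amount. This is one of three endpoints in Panel 4 for the resource-utilisation objective, and the third (flares) is only summarised descriptively. No confirmatory conclusion depends on it.

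**Working it through.** **Figures in the plan.** Section 12.1 gives power only for the primary endpoints. With 123 placebo and 246 tralokinumab subjects, a two-sided 5% level and rates of 15% and 30%, a two-proportion calculation gives 90.2% against the stated 90%. The protocol gives no SD, effect size or power for TCS grams or for diary days, so there is no plan figure to reproduce for this point.

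**Step 1: effect of a baseline covariate.** Let r be the partial correlation of baseline BSA or EASI with grams in a given two-week period, after region and IGA. Adding the covariate multiplies the variance of the treatment difference by about 1 − r², the SE by √(1 − r²), and makes 369 subjects worth 369/(1 − r²) under the planned model. The protocol gives no r, so the range 0 to 0.5 is an assumption.

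| r | Variance reduction | SE reduction | 369 worth | Power* |
|---|---|---|---|---|
| 0 | 0% | 0% | 369 | 80.0% |
| 0.1 | 1% | 0.5% | 373 | 80.4% |
| 0.2 | 4% | 2.0% | 384 | 81.6% |
| 0.3 | 9% | 4.6% | 405 | 83.6% |
| 0.4 | 16% | 8.3% | 439 | 86.4% |
| 0.5 | 25% | 13.4% | 492 | 89.9% |

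*At a difference of 0.31 SD, which has 80% power under the planned covariates with all 369 analysed. This is an illustration only.

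**Step 2: how much IGA already absorbs.** Assume a correlation of 0.3 between extent and grams, 0.5 between extent and IGA, and 0.2 between grams and IGA. Then the partial r = (0.3 − 0.5 × 0.2)/√((1 − 0.25)(1 − 0.04)) = 0.2/0.849 = 0.24, and the saving is 0.24² ≈ 5.6%, not 9%.

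**Step 3: bias check.** In 3,000 simulated trials per setting with a true difference of −0.30, the mean estimate was between −0.296 and −0.301 with or without the covariate. The ratio of SEs, adjusted to unadjusted, was 1.00 at r = 0, 0.96 at r = 0.3 and 0.87 at r = 0.5. The issue is precision, not validity.

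**Step 4: interval length.**

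- First interval (baseline has no window): 14 ± 3 = 11 to 17 days, or 11/14 = 79% to 17/14 = 121% of 14 days.
- Later intervals (a window at both ends): 14 ± 6 = 8 to 20 days, or 8/14 = 57% to 20/14 = 143%.
- If deviations were independent and uniform on the seven days from −3 to +3 (assumption), each has variance (49 − 1)/12 = 4. A later interval then has SD √(4 + 4) = 2.8 days, about 20% of 14. Each extreme (8 or 20 days) has probability (1/7)² = 1/49.
- Because visits are re-planned to baseline, deviations do not accumulate. Over the full 16 weeks (112 days) the end point moves by at most 3 days, 3/112 = 2.7%. The noise affects the two-week amounts, which are what 12.3.7 models, far more than the total.

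**The case against.** The strongest defence is that this is a choice of efficiency and not an error. The model adjusts for both stratification factors, randomisation protects the comparison, and nothing in the protocol contradicts it. All of that stands. These are also additional secondary endpoints outside the hierarchy in 12.3.4.

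The omission has a logic too. In 12.3.6.1 the extra term is the baseline value of the outcome itself. TCS use has no such value, because TCS is washed out for two weeks before randomisation and the supplied product starts at Day 0. A reader might infer that every other continuous endpoint gets a baseline × visit term and that this model is the exception. The protocol does not support that: days of no or slight bother on the PGI-B (12.3.8.2) are also analysed with only treatment, region and baseline IGA.

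A reader might also infer that precision is certainly thrown away. The documents give no correlation, and at r near 0 nothing is gained. Panel 6 separates grades 3 and 4 partly by extent, so IGA takes up some of the gain. As-needed use, and lower-potency products that are not weighed (9.1.3.2), may weaken the link further.

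For days without topical treatment the covariate argument is weak, since a daily yes/no item need not scale with area. The argument from grams per interval does not apply to it.

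On intervals, the 8- and 20-day cases are extremes and cannot occur in the first interval. That a missed visit would double an entry is an inference; the protocol does not say how such an entry is handled. Mapping tube weights to two-week periods could also be left to a later derivation.

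What survives is narrower. The protocol writes out the mean model in full, it has only a two-level disease covariate for an outcome plausibly driven by area, and a better one is already collected.

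**Conclusion.** The point holds for the amount of TCS used, at low priority. Precision is likely lost by leaving out baseline BSA or EASI, and the size cannot be fixed from the protocol: a variance reduction of 0% to 25% is forgone for an assumed partial correlation of 0 to 0.5. Raw grams between visits add avoidable noise to the two-week amounts: at constant daily use they can range from 57% to 143% of the 14-day amount at the extremes, and from 79% to 121% in the first interval. The treatment comparison is unbiased either way, and neither the sample size nor any hierarchical test is affected. For days without topical treatment the case is only that the covariate might help.

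**What to change.** In 12.3.7, change the TCS-amount model to treatment × visit + baseline BSA × visit + region + baseline IGA, with baseline EASI × visit as the alternative. Name one of the two in advance. Define the outcome for each period as 14 × (grams used between two visits)/(days between those visit dates). Adding the covariate to the model for days without topical treatment is optional.

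The cost is one slope per post-baseline visit (eight for Weeks 2 to 16) and one simple derivation step. No new data and no change in conduct are needed. Section 12.3.12 already provides for a blinded review and a finalised analysis plan update before the code is broken, so the change can be made there.

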The initial treatment period (randomisation until Week 16) will be analysed separately from the continuation treatment period (Week 16 until Week 32). All objectives and corresponding endpoints are listed in Panel 4.

Panel 4 Objectives and endpoints

Objectives	Endpoints	
Primary objective	Primary endpoints	
To demonstrate that tralokinumab in combination with TCS is superior to placebo in combination with TCS in treating moderate-to-severe AD.	 IGA score of 0 (clear) or 1 (almost clear) at Week 16. EASI75 at Week 16. 	
Secondary objective	Secondary endpoints	
To evaluate the efficacy of tralokinumab in combination with TCS on severity and extent of AD, itch, and health related quality of life compared with placebo in combination with TCS.	 Severity and extent of AD Change in SCORAD from baseline to Week 16. Itch Reduction of Worst Daily Pruritus NRS (weekly average) of at least 4 from baseline to Week 16. Health-related quality of life Change in DLQI score from baseline to Week 16. 	
Additional secondary objectives	Additional secondary endpoints	
To assess the safety of tralokinumab in combination with TCS when used to treat moderate-to-severe AD for 32 weeks.	 AE/SAE frequency by preferred term. Frequency of anti-drug antibodies. 	
To evaluate the efficacy of tralokinumab in combination with TCS on health care resource utilisation compared with placebo in combination with TCS.	 Amount of TCS used through Week 16 (assessed as the amount of TCS weighted from previous visits). Number of AD flares through Week 16. Number of days without topical treatment use from baseline to Week 16 (according to Patient Days of Topical Treatment Use). 	
To support the primary and secondary objectives in the trial.	 Supporting primary endpoints EASI50 at Week 16. EASI90 at Week 16. Change from baseline to Week 16 in EASI score. Supporting severity and extent of AD SCORAD75 at Week 16. SCORAD50 at Week 16. 	

Trial ID: LP0162-1339	Date: 29-Aug-2018	Version: 4.0
		Page 33 of 129

Panel 4 Objectives and endpoints (continued)

Objectives	Endpoints	
Additional secondary objectives	Additional secondary endpoints	
To support the primary and secondary objectives in the trial (continued).	 Supporting itch Change from baseline to Week 16 in Worst Daily Pruritus NRS (weekly average). Supporting health-related quality of life Reduction from baseline to Week 16 of DLQI of ≥4 points among subjects with baseline DLQI ≥4. 	
Maintenance objective	Maintenance endpoints	

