9.6 Rescue treatment

If medically necessary (i.e., to control intolerable AD symptoms), rescue treatment for AD may be provided to trial subjects at the discretion of the investigator. If possible, investigators should attempt to limit the first step of rescue therapy to topical medications, and escalate to systemic medications only for subjects who do not respond adequately after at least 14 days of topical treatment. The subject will be monitored for signs of local or systemic TCS toxicity and the safety and appropriateness of continued use will be supervised by site staff. For reporting of AD flares see Section 10.3.1.4.

Subjects who receive topical rescue treatment (higher potency TCS: Europe Class >3; US Class <4) will continue IMP treatment.

If a subject receives rescue treatment with systemic corticosteroids or non-steroidal systemic immunosuppressive drugs (cyclosporine, methotrexate, mycophenolate-mofetil, azathioprine, etc.), IMP will be immediately discontinued (see Section 9.7.2, reasons for temporary discontinuation of IMP). After the treatment with these medications is completed, IMP may be resumed if deemed appropriate by the investigator and sponsor's medical expert, but not sooner than 5 half-lives after the last dose of systemic rescue medication.

Investigators should make every attempt to conduct efficacy and safety assessments (at least disease severity scores [IGA and EASI], concomitant medications/procedures, and AEs) immediately before administering any rescue treatment. An unscheduled visit may be used for this purpose, if necessary.

In the primary efficacy analyses, subjects who receive topical or systemic rescue treatment during the treatment periods will be considered as non-responders.

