10.3.2.4 Patient Days of Topical Treatment Use

Subjects will assess their use of topical AD treatment use over the past 24 hours using a response scale ('yes', 'no'). Subjects will complete the Patient Days of Topical Treatment Use as part of an eDiary each day in the morning from baseline (Week 0 [visit 3]) until Week 32. The Patient Days of Topical Treatment Use is included in the investigator trial file.

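### Days without topical treatment serves the resource-utilisation objective, but Section 12.3.7 drops every post-rescue day and states no analysis that keeps them

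*Protocol*

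**What the plan says.** Protocol Section 6, Panel 4, gives this objective: "To evaluate the efficacy of tralokinumab in combination with TCS on health care resource utilisation compared with placebo in combination with TCS". One of its three endpoints is "Number of days without topical treatment use from baseline to Week 16 (according to Patient Days of Topical Treatment Use". The definition is not limited to time before rescue.

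Section 10.3.2.4 describes the diary item: "Subjects will assess their use of topical AD treatment use over the past 24 hours using a response scale", answered yes or no each day. It is not restricted to the supplied TCS. Panel 2 (footnote 7) has it completed daily from Week 0 to Week 32. Panel 3 (footnote 5) keeps the diary going to the nominal Week 16 visit in subjects who stop IMP permanently before then.

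On rescue, Section 9.6 says that, where possible, "investigators should attempt to limit the first step of rescue therapy to topical medications", and that topically rescued subjects stay on IMP. It also covers systemic rescue ("If a subject receives rescue treatment with systemic corticosteroids or non-steroidal systemic immunosuppressive drugs"), for which IMP is stopped and may later be resumed.

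Section 12.3.7 says that TCS amount and days without topical treatment "will be determined by 2-week periods" and are analysed "by a repeated measurements model with an unstructured covariance matrix and the mean modelled as follows", with treatment by visit, region and baseline IGA. It then adds "Results obtained after initiation of rescue treatment will be excluded from the analyses".

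**The concern.** For SCORAD or DLQI, rescue is an outside event that obscures the effect of the randomised treatment, and removing what follows it is a recognisable choice. Here topical rescue is itself an instance of what the endpoint counts. A subject given a higher-potency TCS answers yes in the diary, and that answer is a valid record of topical use under the assigned regimen. Section 12.3.7 removes it.

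At stake is whether the endpoint can answer its own objective. A reader of the trial report would take the result as the difference in topical-free days over 16 weeks between the two regimens. What is estimated is that difference in a setting where nobody could be rescued. The data for the first quantity are collected, yet no planned analysis uses them.

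**Working it through.** **The plan's own figures.** The protocol gives no rescue rate, mean, SD or effect size for this endpoint, so there is nothing to reproduce. Its sizing figures concern the primary endpoints and are not in question.

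**Step 1: what the planned model estimates.** There are 16/2 = 8 two-week periods. For a rescued subject, the periods before rescue stay in and later results are removed. A likelihood-based repeated measurements model then treats the removed values as missing at random. In effect it projects them from subjects in the same arm with similar earlier use who were not rescued. The target is topical-free days without rescue.

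**Step 2: what Panel 4 asks for.** Panel 4 asks for topical-free days from baseline to Week 16 as a measure of resource use. Actual use includes days on topical rescue.

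**Step 3: is the gap filled elsewhere?** A regardless-of-rescue estimand is written for the primary endpoints (12.3.5.3), extended to the binary pruritus endpoint (12.3.6), and written for SCORAD and DLQI (12.3.6.2). None is written for this endpoint.

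**Step 4: can the numerical effect be derived?** No, but it can be illustrated. Every input below is an assumption:
- 40,000 simulated subjects per arm and 8 periods, with counts limited to 0-14 days.
- Mean topical-free days per period rising linearly from 4 to 8 (tralokinumab) and from 4 to 6 (placebo).
- Between-subject SD 3.5 and within-subject SD 2.5.
- Rescue more likely after a period with few topical-free days.
- Post-rescue topical-free days per period with the mean shown and SD 1.

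The table gives the arm difference (tralokinumab minus placebo) summed over Weeks 0-16. Change = excluded - all days.

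| Post-rescue mean (of 14) | Rescue, tralokinumab/placebo | All days kept | Post-rescue excluded | Change |
|---|---|---|---|---|
| 0.5 | 3%/10% | 7.74 | 6.93 | -0.81 |
| 0.5 | 5%/20% | 8.55 | 6.77 | -1.78 |
| 0.5 | 10%/30% | 9.59 | 7.21 | -2.38 |
| 0.5 | 10%/10% | 6.54 | 6.97 | +0.43 |
| 0.5 | 20%/20% | 5.85 | 6.85 | +1.00 |
| 4 | 5%/20% | 6.53 | 6.83 | +0.30 |
| 8 | 5%/20% | 3.86 | 6.58 | +2.72 |
| 8 | 10%/30% | 3.05 | 6.95 | +3.90 |

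With no rescue at all, the same set-up gave 6.98 to 7.49 across four runs, so differences of a few tenths between rows are simulation noise. The comparison within a row is the informative one.

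**Reading the table.** The excluded column stays between 6.58 and 7.21, close to the no-rescue value whatever happens after rescue. That is what a no-rescue estimand should do when data are missing at random, as they are by construction here. The all-days column runs from 3.05 to 9.59. The two analyses answer different questions. Which is larger depends on the rescue imbalance and on topical use after rescue.

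**The case against.** The strongest reply is that the exclusion is a chosen estimand. Section 12.3.7 bases the additional secondary endpoints on the primary analysis of the primary estimand. For continuous endpoints that is the hypothetical one in 12.3.6.1, with no rescue available before Week 16. Excluding post-rescue results is consistent with it, and no bias against that estimand has been shown. This stands: the exclusion is not an error against the estimand the section points to. It does not settle whether that estimand suits a utilisation objective. The fit is also incomplete, since 12.3.6.1 drops data after rescue and after permanent IMP discontinuation, whereas the sentence for this endpoint names rescue only.

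A second reply is that rescue is not lost from the resource objective, because AD flares through Week 16 are summarised with time at risk running to the last visit attended. That is true, but flares count episodes of escalation, not days of topical use.

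A reader might also infer more than the documents support:
- **That the heaviest users leave the analysis as their use peaks.** Their pre-rescue periods remain in the model. The item is yes/no per day, so a subject already treating daily has no topical-free days for rescue to remove.
- **That topical-free days are overstated in both arms, or that the benefit is understated whenever placebo is rescued more.** Systemic rescue is allowed, and topical-free days could rise after it. In the table, 5%/20% rescue gives a lower, nearly unchanged or higher difference, depending only on the post-rescue mean.
- **That a given percentage bias follows from a given placebo rescue rate.** Any such figure rests on an assumed level of post-rescue use, which the protocol does not give.

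**Conclusion.** The point holds as a mismatch between objective and analysis. As written, Section 12.3.7 cannot report topical-free days under the two regimens as treated, although Panel 4 asks for resource utilisation to Week 16 and the diary data are planned to be collected. This conclusion rests on the protocol text alone.

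The numerical consequence is unknown. The scenarios range from -2.4 to +3.9 days over 16 weeks, and they illustrate that the sign is open rather than estimate an effect. The stronger claim, that the arm difference is biased in a known direction, is not supported.

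Importance is limited. This is an additional secondary endpoint outside the testing procedure in Section 12.3.4. The sample size and the primary and confirmatory secondary conclusions do not depend on it. It is a cheap improvement worth making.

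**What to change.** In Section 12.3.7:
1. State the estimand for days without topical treatment, including how rescue and permanent IMP discontinuation are each handled.
2. Add a pre-specified analysis using all diary days to Week 16 regardless of rescue, with topical rescue days counted as the subject recorded them. Report it beside the exclusion analysis.
3. Leave the post-rescue exclusion in place for the TCS-amount endpoint. Weighing covers only the supplied TCS tubes (9.1.3.2, 9.8.3.2), so the weights do not capture rescue products.

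The cost is a short wording change and one more run of the planned model, with no new data collection. The downside is two estimands for one additional secondary endpoint, so it will no longer be handled identically to its paired TCS-amount endpoint. The report should say which result answers the utilisation objective.
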